Each mini-booster consists of four components: 1) collecting information about specific network members that the participant has engaged with about testing/vaccination (both Education/Motivational arm); 2) devising personalized conversational strategies for approaching these network members (C3); 3) troubleshooting communication barriers (C3); and 4) setting personal outreach goals (C3). The Education condition will also have a 30-day follow-up conversation and review of any questions that may come up. Measurement of testing/vaccine barriers for participants and participants' report on network members will be collected during the booster session for both Motivational and Education conditions. The same staff member who provided the initial intervention will conduct the booster with a given participant in order to continue rapport building.

Subject Compensation. Compensation will be provided for study participation- up to \$200 will be provided for study participation and all participants will receive snacks/refreshments during the Education and Motivational arm sessions. Compensation will be provided as follows:

- 1) \$150 will be provided for completing the first study interaction (i.e., consent, ROI, Education or Motivation group session, baseline survey and short locator form);
- 2) \$25 for completing the second study interaction (i.e., short phone booster session and second survey 30 days later); and
- 3) \$25 for completing the third study interaction (i.e., final survey 90 days post enrollment).

Payments will be in cash, gift cards or e-payments such as CashApp, PayPal or Venmo.

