Staff Training and Fidelity. Site teams consisting of existing research staff and community facilitators will deliver the study conditions. Separate staff will deliver the Educational and Motivational intervention group sessions (described below). Site teams will undergo two full day training sessions that include study procedures and group session activities. All research and community facilitators will undergo initial motivational interviewer training with a certified MINT trainer on core motivational interviewing (MI) principals and then monthly follow-up sessions providing clear and objective feedback. In addition, research staff will be trained to have capacity to support multiple participants simultaneously in the self-administered portion of the study visit: clarifying any survey items, troubleshooting any technology/data collection issues, and transitioning to interviewer administered for people with limited literacy. Fidelity to Educational and Motivational intervention conditions will be evaluated using a self-monitoring fidelity check-list for interventionists. A sample of 10% of the sessions will be recorded (video and/or audio) for quality improvement purposes and reviewed by project managers/PIs. These recordings may be shared amongst the respective site-specific study team, but will not be shared outside of the subject's study site). Subjects will be asked whether they are willing to have the session recorded and can indicate yes or no on the study consent form.

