In general, protection against risk to participants will be accomplished through thorough training of research staff; careful orientation of potential participants as to the nature, risk, and benefits of the research; strict adherence to study protocols; and regular surveillance for adverse events. Additionally, this study will receive an NIH Certificate of Confidentiality to further protect information shared.

- The following steps will be taken to protect the confidentiality of all data generated and collected throughout the course of the study:
- Data access will be limited to a specified group of programmers and researchers identified as study personnel. An audit trail will be maintained to track all user-access to the data.
- All study investigators and research team personnel will be trained in the importance of confidentiality and trained to follow all rules related to handling confidential data.
- All data sets resulting from this study will be kept exclusively in the BSD CRI system at the University of Chicago, access to which requires administrative approval and password. The internal server is encrypted at the storage, backup, and sharing levels, thereby maximizing protections against breaches of confidentiality.
- The research team will not be permitted to copy the raw data or to transmit the raw data other than through a secure server connection.
- Results of the study will be reported only in the aggregate and without other identifiable data, with attention to issues of statistical disclosure.

Protection of privacy. All study procedures will be performed in quiet, private spaces to ensure confidentiality. If covid test results and/or vaccine status is communicated via email or text picture using a cell phone, this communication would occur with the subject's site study personnel only. The testing/vaccination data would be recorded and the email/text picture would be deleted. The images

are not retained or shared.

Protection against psychological discomfort. Survey questions may touch on potentially sensitive topics. Participants will be informed of this possibility through assent/consent procedures and they will be reminded that they may skip questions or discontinue participation altogether. If a participant expresses distress directly to the research team, they will be provided the name and contact information of several licensed behavioral health providers on our research team and other local resources as needed.

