Protection against testing risks. Testing Procedures and Infection Control Measures. All COVID-19 testing procedures will take place according to SOPs at each of the participating partnering health departments and clinics. These procedures ensure that appropriate infection control measures, a COVID-19 screener (Appendix C), counseling, including quarantine and isolation procedures, masking and results disclosures are provided in accordance to the current standard of care and CDC guidelines. Monetary, food, other tangible supports, and/or linkage to further medical evaluation and will be provided for individuals who test positive and require resources to adhere to quarantine and social distancing requirements. Performance of surveys and interviews will abide by social distancing guidelines.

Benefits: The potential benefits of this research far outweighs the risks. For individual participants, benefits include COVID-19 testing/vaccination information and reduced likelihood of COVID-19 severe complications and hospitalizations, with provision of financial and other tangible resources for quarantine and isolation as well as linkage to medical care if necessary. Possible risks (i.e. discomfort answering questions, potential confidentiality breaches, stigma) are outweighed by the new knowledge gained as described above and the direct clinical benefits and supportive services to participants.

DATA STORAGE AND SHARING

We will take several steps to ensure the security of the identifiers and data collected for this study. All data will be collected using dedicated laptops purchased by the project and configured and certified by BSDIS to meet their requirements for portable computers (e.g., timed log-out, whole-disk encryption, use of BigFix and antivirus software, etc.). Data will be entered into REDCap (web-based application hosted by the CRI at the University of Chicago). This data will be maintained on a HIPAA compliant, secure server hosted at the University of Chicago.

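### Behavioral-health referral is tied to distress voiced to staff, although depression and anxiety are measured and part of the survey is self-administered; give the referral list to everyone

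*Combined protocol and SAP*

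**What the plan says.** **Referral.** Potential Risks and Benefits to Subjects, under Protection against psychological discomfort, acknowledges that survey questions may be sensitive and lets participants skip them or stop. The referral rule follows: "If a participant expresses distress directly to the research team, they will be provided the name and contact information" of several licensed providers on the team, with other local resources as needed.

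**Mental-health measures.** Other Variables for Analysis lists mental health, with the PHQ-9 as an example, and symptoms of anxiety and depression. Aim 1b names mental health status as a possible effect modifier, and Primary and Secondary Outcome Analysis gives it as an example covariate.

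**Survey mode.** Staff Training and Fidelity says that staff will be trained to "support multiple participants simultaneously in the self-administered portion of the study visit", and to switch to interviewer administration for people with limited literacy. Baseline Surveys also allows completion by telephone or video call.

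**Surveillance.** The opening of Potential Risks and Benefits to Subjects counts "regular surveillance for adverse events" among the protections. Subject Compensation describes the 30-day contact as a "short phone booster session and second survey 30 days later". The Mini-Booster section says that testing and vaccine barriers and reports on network members "will be collected during the booster session for both Motivational and Education conditions". The 3-month contact is described in Study Visit Procedures, Primary Outcomes, and Attrition and missing data.

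**The concern.** The referral rule waits for the participant to speak. The measures most likely to show that someone is struggling may be answered on a laptop while a staff member attends to several people. An answer entered that way is not distress expressed directly to the team, so the rule does not apply to it. The plan describes how these answers will be analyzed but not whether anyone looks at them while the participant is still present.

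What is at stake is participant protection: someone with a severe answer could leave without being told that help is available, although the team already has providers and a list of contacts. A smaller, related matter is that surveillance for adverse events is promised without a described method, and no described follow-up content asks about harm.

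**Working it through.** No figure in the plan bears on this point. The check is a reading of every section that describes mental-health measures, survey mode, referral, adverse events or follow-up contact, plus a small costing.

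**Referral**

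1. *Trigger.* The condition is distress expressed directly to the research team. No score, review or timeframe is attached.
2. *Source of severe answers.* Other Variables for Analysis lists the measures. It says the variables are obtained from a community measures database and does not name the visit. Study Visit Procedures says that the baseline survey carries the variables of interest, so baseline is likely but not stated.
3. *Other support described.* Study Visit Procedures gives everyone, in both arms, COVID-19 testing and vaccination referral information. Protection against testing risks offers resources and medical linkage to people who test positive. Benefits mentions supportive services in general terms. None has a mental-health trigger.
4. *Result.* Followed exactly, the rule offers nothing to a participant who enters severe answers and says nothing.

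**How many people**

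The number affected is 800 × (share answering by self-administration) × (share of those with a severe answer) × (share of those who say nothing to staff). The documents give none of the three shares, so no estimate is made. Telephone, video and interviewer administration reduce the first. The live calls may reduce the third.

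**Harm questions at follow-up**

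| Contact | Content described | Harm question described? |
|---|---|---|
| 30 days, both arms | Network members approached; testing and vaccine barriers | No |
| 30 days, Motivational only | Conversation strategies, communication barriers, outreach goals | No |
| 30 days, Education only | Follow-up conversation and review of questions | No |
| 3 months, both arms | Testing and vaccination uptake, barriers and facilitators, context of testing | No |

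The survey instruments and appendices were not available, so the finding is that a harm question is not described, not that none is asked.

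**Cost of harm items**

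- Inputs: 800 participants, two contacts each, and an assumed 2 to 3 minutes per contact.
- Contacts: 800 × 2 = 1,600.
- Staff time: 1,600 × 2 / 60 = 53.3 hours; 1,600 × 3 / 60 = 80 hours.
- By site (Table 1): 150 × 2 × 2 / 60 = 10 hours to 150 × 2 × 3 / 60 = 15 hours at each 150-person site; 250 × 2 × 2 / 60 = 16.7 hours to 250 × 2 × 3 / 60 = 25 hours at each 250-person site.
- Share of a 10 to 20 minute booster: 2 / 20 = 10% to 3 / 10 = 30%.

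**The case against.** **The argument rests on silence in summary text.** The survey items and appendices might contain a harm question or a score alert. This largely disposes of the surveillance half, which becomes a request for detail. It weighs less against the referral half, because the protocol states a rule there and ties it to one condition.

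**Answers often reach a person.** Telephone, video and interviewer modes put staff in the conversation. At 30 days, "The same staff member who provided the initial intervention will conduct the booster" to build rapport; the Motivational arm works through communication barriers and the Education arm reviews questions. These are real openings for distress to be voiced, and they reduce the number affected. They do not change the condition that the participant must voice it.

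**It is not certain that the PHQ-9 is given at the visit.** It appears only as an example, with no visit named. Depression and anxiety symptoms are listed as well, so the point does not depend on that one instrument.

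**Stronger readings that the documents do not support**

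- A reader might infer that no adverse-event surveillance takes place. Surveillance is promised; only its method is undescribed.
- A reader might object that the Benefits statement, "Possible risks (i.e. discomfort answering questions, potential confidentiality breaches, stigma) are outweighed by the new knowledge gained", could not be checked against trial data. It is an advance risk-benefit judgement, which the trial did not set out to test.
- A reader might want the gap expressed as the harm rate that zero reports could rule out. Such a bound would describe a proposed question, not the amount of harm now missed, which is unknown.

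**Conclusion.** The point holds for referral. As written, behavioral-health contacts depend on distress being voiced to staff, while the plan collects answers that may show the same need without a word being spoken. This is a cheap improvement of minor severity. The number of participants affected cannot be estimated from the documents and may be small.

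The conclusion assumes that the depression and anxiety measures are administered in a study survey, probably at baseline, and that no unsupplied instrument or procedure already acts on severe answers. The surveillance part is secondary and lapses if the instruments already contain suitable harm items. Efficacy outcomes and their planned analyses are unaffected. The referral rule is the same in both arms, so it gives no reason to suspect bias in the comparison.

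**What to change.** **Referral (main change).** Replace the distress-only rule:

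- Give the existing behavioral-health referral list to every participant in both arms, together with the COVID-19 referral information already handed out.
- Keep the active offer to anyone who expresses distress.
- Where a site can score answers during the visit, also make the offer above a threshold set by the team's licensed providers.

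The list costs almost nothing but is passive, because a person in difficulty must still act on it. The score-based offer reaches people who say nothing, but needs same-visit scoring and provider time.

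**Harm items (minor addition).** Unless the instruments already have them, put the same few items in the existing 30-day and 90-day surveys in both arms: distress from taking part, breach of privacy, and conflict or stigma arising from network conversations. Ask them at 30 days before any content specific to the Motivational arm. Since "Separate staff will deliver the Educational and Motivational intervention group sessions" and the booster caller is the person who delivered the intervention, use the 30-day answers mainly to find cases and act on them. Tabulate descriptively by arm, with the number asked and the number answering. Describe the items as one part of the promised surveillance, so that they do not narrow it.

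**Cost.** The items take 53 to 80 staff hours in total under the assumed 2 to 3 minutes. Add staff time to follow up positive answers (not estimated), minor survey programming and consent wording, one table, and a small amendment at the two IRBs of record.
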